17.2 Saint George's Respiratory Questionnaire

The Saint George's Respiratory Questionnaire (SGRQ) is completed at baseline (Day 1), Day 8, Day 15, Day 28, Day 45, and Day 58. The SGRQ is a component-based questionnaire with 3 component scores (Symptoms, Activity, and Impacts) and a total score for all components. The method of calculating all component scores and total score is detailed in the SGRQ manual provided in the Appendix to this SAP.

The questions and response weights used in the scoring algorithm are presented in Section 7 of the SGRQ manual. The responses to Questions 1-8 are used to calculate the Symptoms component score. The Symptoms questions are designed to assess subjects' perception of their respiratory problems over the preceding 3 months. The Activity component score is calculated from the responses to Questions 11 and 15, which measure disturbances to subjects' daily physical activity. The Impacts component score is calculated from the responses to Questions 9-10, 12-14, and 16-17. The Impacts component score assesses disturbances of psycho-social function resulting from subjects' respiratory problems. Subjects who are not receiving respiratory treatment are scored weight values corresponding to a

response of “False” for Question 14. A Total score that summarizes the impact of the disease on overall health status also is calculated. Each component score and the total score are expressed as a percentage of overall impairment where 100 represents the worst possible health status and 0 indicates the best possible health status. No imputation for missing values will be performed. The scoring algorithms account for unanswered questions.

Summary statistics for each component score and total score will be displayed by study drug and all GBT440, and by visit for the Efficacy-Evaluable population. The change from baseline to each post-baseline visit also will be summarized. Self-described current health status (very poor, poor, fair, good, or very good) at each visit will be summarized with the number and percent of subjects in each category. Additionally, subjects receiving respiratory treatment and those who reported other activities stopped by respiratory problems at each visit will be summarized with the number and percent of subjects by study drug and overall.

ANCOVA models will be used to analyze the effect of treatment on the change from baseline with baseline value as a covariate. Least squares (LS) means and SEs will be displayed for the change from baseline in each treatment group and for all GBT440.

LS means (95% CI) and p-values from the models will be used to make the following comparisons:

- GBT440 600 mg – Placebo
- GBT440-900 mg – Placebo
- GBT440-1500 mg – Placebo
- All GBT 440 – Placebo

Component scores and total score, self-described health status, receiving respiratory treatment, and other activities stopped by respiratory problems will be provided in a subject listing of SGRQ results.

17.3 UCSD Shortness of Breath Questionnaire

The UCSD Shortness of Breath Questionnaire is completed at Baseline (Day 1), Day 8, Day 15, Day 28, Day 45, and Day 58. The questionnaire is comprised of 24 questions each scored on a scale of 0 to 5. Total score ranges from 0 to 120 where higher scores indicate worse severity due to shortness of breath. Scores for each question answered will be summed to provide a total score. Missing responses are not included in the calculation of the total score.

Summary statistics for the UCSD Shortness of Breath Questionnaire total score will be displayed by study drug and all GBT440, and by visit for the Efficacy-Evaluable population using actual data collected at the site. The change and percent change from baseline to each post-baseline visit also will be summarized and displayed.

ANCOVA models will be used to analyze the effect of treatment on the change from baseline with baseline value as a covariate. Least squares (LS) means and SEs will be displayed for the change from baseline in each treatment group and for all GBT440.

LS means (95% CI) and p-values from the models will be used to make the following comparisons:

- GBT440 600 mg – Placebo
- GBT440-900 mg – Placebo
- GBT440-1500 mg – Placebo
- All GBT 440 – Placebo

Total scores will be provided in a subject listing of UCSD Shortness of Breath Questionnaire results.

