4. STUDY POPULATION

4.1. Inclusion Criteria

All subjects must meet the following inclusion criteria:

1. Able and willing to provide signed informed consent to participate in this study.
2. Documented diagnosis of IPF, as indicated in the ATS/ERS/JRS/ALAT 2011 guidelines.
3. Adult males or females aged 45–80 years inclusive at randomization.
4. Oxygen saturation (SpO₂) ≥88 % by pulse oximetry while breathing room air at rest.
5. Oxygen saturation (SpO₂) <88% and at least a 5% absolute decrease during the baseline 6MWT which is sustained for at least 10 seconds.
6. Able to walk a total of at least 100 meters at completion of the baseline 6MWT.
7. Weight ≥ 40 kg
8. Subject is seronegative for hepatitis A (IgM anti-HAV), hepatitis B surface antigen (HBsAg), hepatitis C antibody (anti-HCV), and human immunodeficiency virus antibody (anti-HIV) within 3 months of screening.
9. Able, in the Investigator's opinion, to complete the 6MWT unassisted at baseline and Day 15 and Day 28 and comply with the study procedures, including attending all assessment visits and adhering to all study requirements and restrictions.
10. Male or female of child bearing potential willing and able to use highly effective methods of contraception from study start to 3 months after the last dose of study drug.

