5.5.5. Patient Reported Outcome (PRO) Measures

PRO assessments should be self-administered by the subject, using the paper questionnaires provided by the Sponsor, at the investigational site prior to all other non-PRO assessments (except in cases when the screening 6MWT is being repeated on Day 1 prior to any Day 1 visit assessments) and before the patient receives any disease-status information during that assessment. They will be administered as indicated in the schedule of assessments ([Appendix A](#)).

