5.5.5.2. University of California, San Diego Shortness of Breath Questionnaire (UCSD)

The UCSD is a 24-item assessment of breathlessness associated with various activities of daily living. The response for each item is measured on a 5-point Likert scale from 0 (none at all) to 5 (maximal or unable to perform). Paper questionnaires will be provided to sites prior to subject enrollment.

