10.1.2 Stop dates (e.g., AE resolution date or stop date of medication)

- For missing stop day only - Day will be imputed as the last day of the month (i.e., 28, 29, 30, or 31)
- For missing stop day and month - Day and month will be imputed as the last day of the year (i.e., 31 December)

Any partial dates will be displayed in data listings without imputation of missing days and/or months (e.g., MAR2011, 2009). No other imputation of missing data will be performed.

No imputation methods will be used for analysis of missing efficacy data in this study.

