15.2.4 Clinical Laboratory Results

Clinical laboratory data including serum chemistry, liver function tests, serum hematology, serum erythropoietin, coagulation panel, and urinalysis are collected at specified visits. The quantitative variables will be summarized by study drug and all GT440 with continuous descriptive statistics for each visit in the Safety population. Urinalysis results will be presented only as a subject listing. Change from baseline and the percent change from baseline will also be summarized by study drug and all GBT 440. Units for laboratory results will be converted from reported units to SI units in the SDTM datasets. Reported results and units will be used for the summary tables.

Subject listings of laboratory data will include a separate listing for clinically significant laboratory values in addition to subject listings of all laboratory values. Listings will be presented with reported units and SI units. Pregnancy test results for both serum and urinalysis sampling will be provided in a separate listing.

16. Secondary Analyses of 6-Minute Walk Test

The 6-Minute Walk Test is a multiple period assessment that includes a resting period (first minute before the walking portion), the 6-minute walking period, and a post-walking period that includes results at each minute for 2 minutes upon completion of walking. End of exercise is defined as last SpO₂ immediately at end of 6MWT (not including the post-walking period). Blood pressure is collected at rest

and at each minute post walking. The distance walked (meters) is recorded at the end of the walking period.

Results of the 6-Minute Walk test (6MWT) will be summarized by study drug and all GBT440 at the following visits: Baseline (Screening or repeat at Day 1 if applicable), Day 15, Day 28, and Day 58. The number and percentage of subjects in each treatment group and all GBT 440 who completed the 6MWT, experienced myocardial infarction (MI) or unstable angina in the previous 30 days before the 6MWT, and utilized oxygen during the 6MWT will be summarized. Summary statistics (N, mean, SD, median, min, and max) will be displayed for systolic and diastolic blood pressure collected at rest and at each minute post-walking.

Subject listings will be provided for all 6MWT data collected on the eCRF.

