Summary statistics for resting SpO₂, SpO₂ at end of the 6MWT (last available result) and lowest SpO₂ collected during the 6MWT will be summarized at each visit by study drug and all GBT440 in the Efficacy-Evaluable population. Summary statistics for the change and percent change from baseline to Day 15, Day 28, and Day 58 also will be displayed.

Analysis of covariance models (ANCOVA) will be used to analyze the effect of treatment on the change from baseline and the percent change from baseline for each secondary endpoint with baseline value as a covariate. Least squares (LS) means and SEs will be displayed for the change and percent change from baseline in each treatment group and for all GBT440.

LS means (95% CI) and p-values from the models will be used to make the following comparisons:

- GBT440 600 mg – Placebo
- GBT440-900 mg – Placebo
- GBT440-1500 mg – Placebo
- All GBT 440 – Placebo

17. Exploratory Analyses

17.1 6-Minute Walk Test

Summary statistics for the distance walked (meters) during the 6MWT, time to the first SpO₂ < 88%, and AUC of SpO₂ will be summarized by study drug and all GBT 440, and visit in the Efficacy-Evaluable population. The change and percent change from baseline to Day 15, Day 28, and Day 58 in distance walked also will be summarized and displayed.

The AUC of SpO₂ measurements will be calculated for each subject's data at baseline, Day 15, Day 28, and Day 58. The AUC will be estimated using the trapezoid rule for data collected on the eCRF as follows:

$$AUC = \left\{ \sum_{t=1}^n \frac{1}{2} [(Time_t - Time_{t-1}) \times (SpO2_t + SpO2_{t-1})] \right\}$$

where n is the number of measurements of SpO₂ collected during the 6MWT, t is the elapsed time in minutes (nominal time) and SpO₂ is the measurement of SpO₂ level at the respective timepoint, and Time is the timepoint. If a SpO₂ measurement is missing during the 6MWT, then that timepoint is removed from the calculation, such that the AUC is calculated using the trapezoid rule from the 2 timepoints surrounding the missing SpO₂ measurement.

Additional exploratory endpoints include the change from rest to end of 6MWT and change from rest to lowest SpO₂. Both endpoints will be summarized by study drug and all GBT440.

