ANCOVA models will be used to analyze the effect of treatment on the change from baseline for each exploratory endpoint with baseline value as a covariate. Least squares (LS) means and SEs will be displayed for the change from baseline in each treatment group and for all GBT440. Similar ANCOVA models will be constructed for percent change from baseline for AUC and distance walked.

LS means (95% CI) and p-values from the models will be used to make the following comparisons:

- GBT440 600 mg – Placebo
- GBT440-900 mg – Placebo
- GBT440-1500 mg – Placebo
- All GBT 440 – Placebo

All exploratory efficacy data will be provided in subject listings.

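### SAP 17.3 counts each skipped UCSD item as 0, the best answer; SAP 17.1 also lacks a rule for walks that never fall below 88% and for walks that stop early

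*SAP*

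**What the plan says.** **UCSD.** SAP 17.3 describes 24 questions scored 0 to 5, a total of 0 to 120 with higher meaning worse, and a total formed by summing the answered questions. It adds: "Missing responses are not included in the calculation of the total score". There is no rescaling and no minimum number of answered items. Protocol 5.5.5.2 anchors each item "from 0 (none at all) to 5 (maximal or unable to perform"). Protocol 5.5.5 makes the forms self-completed on paper: "PRO assessments should be self-administered by the subject, using the paper questionnaires provided by the Sponsor". The general rule in SAP 10.1.2 is "No imputation methods will be used for analysis of missing efficacy data in this study".

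**Walk test.** SAP 17.1 summarises time to first SpO2 below 88% and the SpO2 AUC. It uses ANCOVA to "analyze the effect of treatment on the change from baseline for each exploratory endpoint with baseline value as a covariate". The AUC is a trapezoid sum that is not divided by time. If a reading is missing, "then that timepoint is removed from the calculation, such that the AUC is calculated using the trapezoid rule from the 2 timepoints surrounding" the gap. Protocol 4.1 requires SpO2 below 88% and "at least a 5% absolute decrease during the baseline 6MWT which is sustained for at least 10 seconds". SAP 19 drops the 10-second condition from the time endpoint because SpO2 was not recorded in seconds. Protocol 5.5.3 says the walk should be stopped if oxygen is given for safety. SAP 16 takes end-of-exercise SpO2 as the last value "immediately at end of 6MWT (not including the post-walking period").

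**The concern.** Leaving an item out of an unscaled sum is arithmetically the same as scoring it 0. The SAP therefore says that nothing is imputed, yet in effect it fills every blank UCSD item with the most favourable answer. A subject whose breathlessness has not changed appears better if items are skipped after baseline, and worse if they are skipped at baseline. The other multi-item scales do not share the problem on their face. SAP 17.2 says the SGRQ algorithm allows for unanswered questions, and SAP 17.6 expresses ATAQ domains as percentages from observed data. (The scoring appendices for those two are not in the text available, so they were not checked.)

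In the walk test, a follow-up walk that stays at or above 88% is a favourable result with no time to record. A walk that stops early gives a smaller AUC simply because fewer minutes are added up. SAP 17.1 and 17.3 attach confidence intervals and p-values for four comparisons to these endpoints, in arms of about 6 to 9 subjects, so a few forms or walks can matter. SAP 6.3 has the sponsor and the CRO statistician unblinded in Part B, so a rule chosen at analysis would be chosen with allocation known.

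**Working it through.** **Inputs.** From SAP 17.3: 24 items, each 0 to 5. From Protocol 3.1 with the pooling in SAP 10.3: 600 mg 6 + 3 = 9, placebo 6 + 3 = 9, 1500 mg 9, 900 mg 6. The documents give no skip rate, early-stop rate, UCSD mean or SpO2 profile, so those used below are assumptions.

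**1. The plan's own figure.** 24 × 5 = 120, as stated. With k items skipped the highest attainable total is 5 × (24 − k): 115, 110 and 100 for k = 1, 2 and 4.

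**2. Effect on one subject.** Assume the skipped items equal the subject's mean item score. Skipping after baseline changes the total by −k/24. Skipping only at baseline gives an apparent change of 24/(24 − k) − 1.

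| Items skipped | After baseline | At baseline only | Points lost after baseline, true total 40 / 60 / 80 |
|---|---|---|---|
| 1 | −4.2% | +4.3% | 1.7 / 2.5 / 3.3 |
| 2 | −8.3% | +9.1% | 3.3 / 5.0 / 6.7 |
| 4 | −16.7% | +20.0% | 6.7 / 10.0 / 13.3 |

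**3. Effect on an arm mean.** One skipped item in one subject lowers the mean by at most 5/9 = 0.56 points in a 9-subject arm, or 5/6 = 0.83 in the 900 mg arm.

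**4. Equal random skipping.** Assume 1%, 2% or 5% of items are skipped at both visits in all arms, with a true total of 60 (item score 2.5). The mean loss per visit is 60p = 0.6, 1.2 or 3.0 points, which cancels in the change. The noise added to each subject's change has SD √(2 × 24 × 2.5² × p(1 − p)) = 1.7, 2.4 or 3.8 points. Letting item scores vary within a subject (SD about 1.2; simulation of 200,000 subjects) gives 1.9, 2.7 or 4.2 for the plain sum, against 0.9, 1.2 or 2.0 after proration.

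**5. Time to first SpO2 below 88%.** No arithmetic is needed. A completed follow-up walk that never falls below 88% has no time, and neither has a walk stopped before it does. SAP 17.1 assigns no value to either. If SAP 10.1.2 is read as dropping them, they leave both the summary and the ANCOVA. The baseline time can be missing too: a qualifying 10-second dip may fall between recorded readings.

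**6. SpO2 AUC.** Assume readings 93, 91, 89, 88, 87, 86, 85 at minutes 0 to 6.
- Full walk: (93 + 85)/2 + 91 + 89 + 88 + 87 + 86 = 530.
- Stop at minute 4: (93 + 87)/2 + 91 + 89 + 88 = 358, which is 32% lower.
- Stops at minutes 5 and 3: 444.5 and 270.5.
- For comparison, a 3-point gain held for the whole walk adds 3 × 6 = 18.
- Time averages: 530/6 = 88.3 for the full walk and 358/4 = 89.5 for the stop at minute 4. Carrying the last reading to minute 6 gives (358 + 2 × 87)/6 = 88.7.

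This takes the AUC over the walk only, the natural reading of SAP 3.2 and 16. SAP 17.1 does not state the window. With assumed post-walk readings of 88 and 91 added at elapsed time, the stop gives 358 + 87.5 + 89.5 = 535, against 530 + 86.5 + 89.5 = 706. Placed instead at fixed minutes 7 and 8, they would let the missing-reading rule bridge the gap: 358 + 3 × 87.5 + 89.5 = 710. The window therefore has to be stated.

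**7. Secondary endpoints.** In the same profile a stop at minute 4 gives an end-of-walk and a lowest SpO2 of 87, against 85 for the full walk: 2 points better because the walk was shorter.

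**The case against.** The case for leaving this alone is that everything here is exploratory apart from the effect on two secondary endpoints. SAP 3.4 sets no formal hypotheses, and the sample size has no statistical basis. One skipped item moves a 9-subject mean by at most 0.56 on a 120-point scale, and equal skipping cancels on average. Data queries (SAP 8) and subject listings (SAP 10.3) would expose blanks. In the walk test, a never-below walk still counts fully in lowest SpO2, completion and oxygen use are tabulated (SAP 16), and all walk data are listed. A low AUC after a stop for oxygen also points in a plausible direction, whereas dividing by time makes the stopper look better.

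Much of this stands, and it limits the size of the problem. It does not repair the UCSD rule: queries and listings show a blank but cannot fill it, and the stated sum still treats it as 0. The objection to a bare time-averaged AUC also stands, and the fix takes account of it.

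A reader might go further and infer that the UCSD rule favours the drug. The documents do not support that: the direction depends on which visit and which arm the blanks fall in. A reader might also infer that the plan discards its strongest responders. The SAP does not say never-below walks are dropped; that is one reading of its no-imputation sentence. How far dropping them would distort the comparison cannot be judged from the documents, because any alternative value, such as 6 minutes, is itself a convention.

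**Conclusion.** The UCSD point holds and should be fixed. SAP 17.3 states a rule that gives a wrong total whenever an item with a true score above 0 is left blank. The loss of 0 to 5 points per item follows from the stated scale alone. The percentages assume equal item scores, and the noise figures assume random skipping at 1% to 5%. Since the true skip rate is unknown and the endpoint is exploratory, the expected impact is modest.

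The two walk-test points are real but smaller: they are missing rules, not wrong ones. The AUC figures rest on one assumed profile. It would be a mistake to treat the secondary SpO2 endpoints as untouched. Resting SpO2 is taken before the walk, but end-of-walk and lowest SpO2 both come from the truncated walk when it stops early. The primary endpoint, adverse events and tolerability, is unaffected.

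**What to change.** **UCSD (SAP 17.3).** Replace the missing-response sentence with: the total is the mean of the answered items times 24 if at least half of the items are answered, and is otherwise missing. The sponsor should set the threshold. List this as an exception to the no-imputation rule in SAP 10.1.2.

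**Time to below 88% (SAP 17.1).** State how completed never-below walks, early-stopped walks and missing baseline times enter the analysis. One option is a rank-based analysis with completed never-below walks ranked best and a separate rule for early stops. Protocol 11.3.2 already allows Wilcoxon's test, so ranks are within its framework.

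**AUC (SAP 17.1).** State the time window and an early-stop rule, and add a sensitivity analysis such as carrying the last walk reading to minute 6. Do not rely on a time average alone. Show the result beside walk completion and oxygen use. Note in SAP 16 that early stops also affect end-of-walk and lowest SpO2. Any value assigned under these walk-test rules should also be a stated exception in SAP 10.1.2.

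**Cost.** SAP wording and programming, with no new data provided that item responses and minute readings are in the database, as the scoring and AUC formulas imply. The completeness threshold is a choice. Proration removes only about half of the added noise, and it still understates if the worst items are skipped: with two skipped items truly 5 and the other 22 averaging 2.5, the true total is 65, the plain sum 55 and the prorated total 55/22 × 24 = 60. A rank analysis gives up a mean difference in minutes.

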17.4 Borg Dyspnea Score during the 6-Minute Walk Test

The Borg dyspnea score will be assessed as the subject performs the 6MWT at the beginning of the rest period, at minute 3 during the walking period, at post-walking minute 1, and at post-walking minute 2. The Borg dyspnea score ranges from 0 to 10 with 0 being no breathing difficulty and 10 being maximal breathing difficulty. Summary statistics for the Borg dyspnea score will be presented by study drug and all GBT440 for each visit and timepoint for the Efficacy-Evaluable population. Summary statistics for the change from baseline to Day 15, Day 28, and Day 58 will also be summarized.

ANCOVA models will be used to analyze the effect of treatment on the change from baseline with baseline value as a covariate. Least squares (LS) means and SEs will be displayed for the change from baseline in each treatment group and for all GBT440.

LS means (95% CI) and p-values from the models will be used to make the following comparisons:

- GBT440 600 mg – Placebo
- GBT440-900 mg – Placebo
- GBT440-1500 mg – Placebo
- All GBT 440 – Placebo

Borg dyspnea scores will be provided in subject listings of the 6MWT for each visit and timepoint.

17.5 Cough Visual Analog Scale

The Cough VAS is completed at Baseline (Day 1), Day 8, Day 15, Day 28, Day 45, and Day 58. The VAS is scored from 0 to 100 where 0 represents no symptom and 100 represents the worst symptom.

Summary statistics for the Cough VAS will be displayed by study drug and all GBT440, and by visit for the Efficacy-Evaluable population using actual data collected at the site. The change from baseline to each post-baseline visit also will be summarized.

ANCOVA models will be used to analyze the effect of treatment on the change from baseline with baseline value as a covariate. Least squares (LS) means and SEs will be displayed for the change from baseline in each treatment group and for all GBT440.

LS means (95% CI) and p-values from the models will be used to make the following comparisons:

- GBT440 600 mg – Placebo
- GBT440-900 mg – Placebo
- GBT440-1500 mg – Placebo
- All GBT 440 – Placebo

